4.2.1. Study Population Rationale

This study will focus on the age group most at risk from accidental exposure to food allergens (pediatric subjects \geq 4 to < 18 years of age) (Cherkaoui, 2015; Coffman, 2015), while allowing for older subjects (\geq 18 to \leq 55 years old) who are motivated to seek desensitization to be included as an exploratory population. While the efficacy endpoint will be analyzed in the pediatric population, safety and efficacy data will be collected and explored in the adult population, given the prevalence of adult subjects with FAs and the different profile of allergies seen specifically; evidence suggests that certain FAs (e.g., shellfish and finfish) may be more likely than others to develop during adulthood (Gupta, 2019).

The lower age limit of 4 years was selected based on epidemiologic child-developmental considerations related to feeding behavior (Farrow, 2012), as well as practical clinical study execution considerations and safety. The upper age limit of 55 years was selected to reduce the chance of enrolling subjects with clinically significant heart disease (Mozaffarian, 2015) who could be at increased risk of serious side effects from the use of epinephrine if needed to treat anaphylaxis. This is particularly relevant in the clinical study setting, in which the potential risk of anaphylaxis and/or epinephrine use may be increased due to both study drug and study procedures (e.g., the requirement for a repeated DBPCFC).

The emphasis on the pediatric subject population is also predicated on results from the PALISADE study (Vickery, 2018), in which the efficacy of AR101 was only demonstrated in subjects under 18 years of age and did not reach significance in subjects 18 to 55 years old, in part due to a high dropout rate in the adult population.

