3.2. Sample Size Determination

The total sample size required is 48 subjects (16:16:8:8) (high-dose ADP101: low-dose ADP101: high-dose placebo: low-dose placebo) for the study. Assuming a 20% pediatric subject dropout rate based on the dropout rate observed in prior oral immunotherapy (OIT) studies, a total of 60 pediatric subjects will be randomized 2:2:1:1 into the 4 arms. The planned randomization scheme is anticipated to enable completion through Week 40 for 16 subjects in each active dose regimen, and a total of 16 subjects taking placebo (8 per placebo dose regimen).

The adequacy of the sample size was confirmed by performing simulations for power calculations using the Fisher's exact test for each of 2 doses (vs. placebo) under alternative hypotheses. Assuming placebo response rates of 4% and active response rates of 40% and 58% in the low- and high-dose regimen treatment groups, respectively (based on [\(Vickery, 2018\)](#)), and an alpha of 5%, power was calculated using the Simes global test ([Simes, 1986](#)) with the Holm procedure ([Holm, 1979](#)) to reject at least 1 of the doses. Results showed approximately 90% power to detect a statistically significant ADP101 response in at least 1 of the doses with the given sample size.

Additionally, a total of approximately 12 adult subjects will be randomized to the 2 doses of ADP101 (approximately 4 subjects on each of the high- and low-dose regimens and 4 subjects on placebo), to provide an initial exploration of the safety and efficacy in this population, as well as the feasibility of enrolling adult subjects in subsequent studies with ADP101. Thus, a total of approximately 72 subjects will be enrolled in this study.

The sample size for the study is sufficient to test the superiority of ADP101 over placebo for pediatric subjects aged ≥ 4 to < 18 years who tolerate at least 600 mg on the Exit DBPCFC of a single qualifying food source within ADP101 without dose-limiting symptoms after 40 weeks of treatment (primary efficacy endpoint) with at least 1 of the 2 dosing regimens (low/1500 mg or high/4500 mg).

A claim of statistical significance will be not be made for the primary endpoint unless the superiority of ADP101 over placebo is demonstrated in at least 1 of the 2 doses (treatment groups).

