3.3. Randomization

All subjects will be centrally randomized in a 2:2:1:1 ratio to 1 of 4 treatments, with 2 treatments in each dosing regimen (low or high), to receive daily oral doses of study drug (either ADP101 or matching placebo) in a blinded fashion using interactive response technology (IRT). The randomization schedule will be generated by an independent unblinded statistician from Syneos Health using SAS® software. The randomization schedule will be managed in the Suvoda IRT system. Randomization will be stratified by age group (≥ 4 to < 18 years of age and ≥ 18 to ≤ 55 years of age). Before the study is initiated, the access directions for the Suvoda IRT will be provided to each site. If a subject fails updosing after 3 consecutive attempts of study drug at 5

mg, an additional subject will be randomized to the study without impacting the overall 2:2:1:1 randomization ratio.

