- All tests of treatment effect will be conducted at a 2-sided alpha level of 0.05, unless otherwise stated. Any confidence intervals (CIs) of the statistical models will be rounded to 1 decimal place. All model estimates, such as least-squares (LS) means if applicable, will be rounded to 2 decimal places. Any calculated p-values will be rounded to 3 decimal places; p-values less than 0.001 will be presented as 'p < 0.001' and p-values greater than 0.999 will be presented as 'p > 0.999'.
- Multiple assessments at a given time point (planned, repeat, and unscheduled) will not be included in summary tables unless specified otherwise, but will be included in the listings. All assessments will be used in analysis of maximum changes or shift analyses.

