In addition to the analyses described above, the following supportive analyses will be performed using the primary endpoint:

- The Farrington-Manning non-inferiority test will be used to compare the primary endpoint response rates of high-dose ADP101 vs. pooled placebo and low-dose ADP101 vs. pooled placebo using a margin of inferiority of 15%.
- The comparison of the primary endpoint between the pooled ADP101 vs. pooled ADP101 will be provided using the Fisher's exact test.
- The analysis of the primary endpoint will be performed for 2 additional populations, 1) all subjects (pediatric and adult subjects combined) and 2) adult subjects in the ITT Population. The same method as described in the primary analysis above (for pediatric subjects) will be used for all subjects and the unadjusted p-values will be reported. Descriptive statistics corresponding to the primary endpoint response rates will be reported for adult subjects.

The plots of subjects with a ≥ 600 mg desensitization response will be provided for pediatric, adult and all subjects in the ITT population and pediatric subjects in the PP population.

Subgroup Analysis

Subgroups of ITT subjects who reached their target dose as their maintenance dose (see Section 6.7) will be analyzed for the primary endpoint. The subjects with ≥ 600 mg desensitization response by reached target dose will be plotted for pediatric subjects in the ITT population.

The 15 ADP101 individual foods will be consolidated into 9 foods/food groups, including peanut, tree nuts (almond, cashew, hazelnut, pecan, pistachio, or walnut), milk, egg, soy, wheat, shrimp, finfish (codfish or salmon), and sesame. Descriptive statistics, such as response rate differences and corresponding 95% CIs, will be provided for each ADP-101 food/food group above as long as there is sufficient sample size in that food/food group. The response rate for each food/food group will be based on the number of subjects with qualifying food allergies within the category.

Supplemental Analyses using the Estimand Framework

The primary and top secondary endpoint will be analyzed using the Estimand framework outlined in the E9(R1) (Statistical Principles for Clinical Trials: Addendum: Estimands and Sensitivity Analysis in Clinical Trials) guidance. The intercurrent event of interest is study discontinuation without completing the exit DBPCFC for any of the subject's qualifying food allergies.

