7.8.2. Secondary Efficacy Endpoints and Analysis

The primary analysis of the secondary endpoints will be performed on pediatric subjects in the ITT Population by treatment group. The analysis will be repeated for the PP Population and relevant subgroups (i.e., subjects who reached 1500 mg of study drug for low-dose group, and subjects who reached 4500 mg of study drug for high-dose group). The analysis will be repeated for all subjects in the ITT Population as well. Descriptive statistics corresponding to the endpoint response rates will be provided for adult subjects. The secondary endpoints will also be analyzed for pediatric subjects in the ITT Population using logistic regression model. The comparison of the secondary endpoints between the pooled ADP101 vs pooled ADP101 will be provided as well.

The secondary endpoints are outlined below:

- Number and percent of subjects who tolerate the 1000-mg level of a single Qualifying Food without dose-limiting symptoms at the Exit DBPCFC (i.e., ≥ 1000 mg desensitization response)
- Number and percent of subjects with ≥ 2 qualifying FAs who tolerate the 600-mg level of each of 2 or more Qualifying Foods without dose-limiting symptoms at the Exit DBPCFC
- Number and percent of subjects with ≥ 2 qualifying FAs who tolerate the 1000-mg level of each of 2 or more Qualifying Foods without dose-limiting symptoms at the Exit DBPCFC

The analyses of the secondary efficacy endpoints will follow the method of the primary efficacy endpoint as described in Section 7.8.1. For these analyses, only the p-values from the Fisher's exact test will be displayed.

The same analyses will be performed on the ITT Population excluding subjects who withdrew from the study prior to completing the Exit DBPCFC for reasons related to COVID-19 (e.g., study site closure).

The last two endpoints will be conducted in the ITT Population, PP Population and relevant subgroups for multi-allergic subjects only.

The plots of each secondary endpoint will be provided for pediatric, adult and all subjects in the ITT population and pediatric subjects in the PP population. The subjects with ≥ 1000 mg desensitization response by reached target dose will be plotted for pediatric subjects in the ITT population.

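### The supportive all-subjects analysis of the primary endpoint leaves out age group, the only randomization stratum; stratifying the difference and its interval is a small improvement at almost no cost

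*SAP*

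**What the plan says.** SAP 3.3 has one stratification factor: "Randomization will be stratified by age group", the groups being 4 to under 18 years and 18 to 55 years. The primary analysis in SAP 7.8.1 is restricted to pediatric ITT subjects. Each dose is compared with pooled placebo by Fisher's exact test, and a Newcombe interval is taken from one treatment-by-endpoint table (the sample code also requests a continuity correction).

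The Supportive Analyses paragraph of 7.8.1 extends this to children and adults together: "The same method as described in the primary analysis above (for pediatric subjects) will be used for all subjects". P-values there are unadjusted, and adults alone are described without testing. SAP 7.8.2 does likewise for the secondary endpoints: "The analysis will be repeated for all subjects in the ITT Population as well". For those endpoints only Fisher p-values are to be displayed.

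The logistic models in 7.8.1 and 7.8.2 are limited to pediatric subjects, so no planned all-subjects efficacy comparison takes account of the age stratum.

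**The concern.** An analysis normally reflects the factor used to stratify randomization. When strata with different response rates are merged into one table, the between-stratum difference enters the variance and the interval becomes wider than necessary. If the small adult stratum ends up unevenly divided, the crude difference also mixes some age effect with the treatment effect.

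There is some reason to think age may matter. Protocol 4.2.1 notes that in an earlier peanut immunotherapy trial efficacy "did not reach significance in subjects 18 to 55 years old", partly because of adult dropout. In this trial, subjects without an Exit challenge count as failures, so dropout enters the endpoint directly. What is at stake is the precision and clarity of one supportive estimate. The primary result is not affected.

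**Working it through.** **The plan's own figure.** SAP 3.2 gives a power calculation for the pediatric comparison: "Assuming placebo response rates of 4% and active response rates of 40% and 58% in the low- and high-dose regimen treatment groups, respectively", with the conclusion "Results showed approximately 90% power to detect a statistically significant ADP101 response in at least 1 of the doses with the given sample size". Exact enumeration of two-sided Fisher tests at 0.05, with 16 per active arm against pooled placebo of 8 + 8 = 16, gives 0.900 with Holm and 0.909 with Simes. The figure reproduces. It concerns children only; the documents give no figure for the all-subjects analysis.

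**Inputs for all subjects.**
- Group sizes: 20 children + 4 adults in each of low dose, high dose and pooled placebo (SAP Table 1, 3.2 and 6.6).
- Child rates: 58% (high), 40% (low), 4% (placebo), from SAP 3.2.
- Adult rates: not given. Assumed 4% on placebo, and from 4% up to the child rate on active.

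**Step 1: width.** Write p for active and q for placebo.
- Unstratified: p = (20·p_child + 4·p_adult)/24, variance = p(1−p)/24 + q(1−q)/24.
- Stratified: Mantel-Haenszel weights are proportional to n·m/(n+m). These are 20·20/40 = 10 for children and 4·4/8 = 2 for adults, so 5/6 and 1/6. Variance = Σ w²[p(1−p)/n + q(1−q)/m].

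High dose, adults at 4%:
- Unstratified: p = (11.6 + 0.16)/24 = 0.49. Variance = 0.49·0.51/24 + 0.04·0.96/24 = 0.01201. Half-width = 1.96·√0.01201 = 0.2148.
- Stratified: (25/36)(0.58·0.42/20 + 0.04·0.96/20) + (1/36)(2·0.04·0.96/4) = 0.00979 + 0.00053 = 0.01033. Half-width 0.1992.
- Ratio 1.079.

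| Child active | Adult active | Unstratified half-width | Stratified half-width | Ratio |
|---|---|---|---|---|
| 58% | 58% | 0.2125 | 0.2125 | 1.000 |
| 58% | 40% | 0.2139 | 0.2122 | 1.008 |
| 58% | 20% | 0.2147 | 0.2071 | 1.037 |
| 58% | 4% | 0.2148 | 0.1992 | 1.079 |
| 40% | 40% | 0.2111 | 0.2111 | 1.000 |
| 40% | 20% | 0.2081 | 0.2060 | 1.010 |
| 40% | 4% | 0.2051 | 0.1979 | 1.036 |

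**Step 2: the same comparison with Newcombe intervals.** By exact enumeration without continuity correction, the expected full width is 1% to 4% greater unstratified (for example 0.427 against 0.415 at 58% and 20%). Coverage of the unstratified interval is 95% to 97%. The continuity correction in the sample code takes 0.427 to 0.479, about 12% wider, with coverage near 98%. The correction therefore costs more width than the missing stratum.

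**Step 3: shift in the difference, high dose, placebo 4% in both ages.**
- Adults 4:4: the crude and Mantel-Haenszel differences coincide, so the shift is 0.
- Adults 5:3, adult active rate 4%: crude = (11.6 + 0.2)/25 − 0.04 = 0.432. Weights are 10 and 15/8 = 1.875, so the stratified difference = (10/11.875)·0.54 + 0 = 0.4547. Shift −2.3 points.
- Adults 5:3, adult active rate 40%: 0.504 against 0.5116, shift −0.8 points.
- Part of the −2.3 arises because 5:3 also changes the Mantel-Haenszel weights. Against the planned 5:1 age mix (0.45) the crude difference is off by −1.8 points.

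**Step 4: shift when there is no treatment effect, adults 5:3.** The adult share differs by 5/25 − 3/23 = 0.0696. With children at the SAP's 4% and adults at 0% in both arms, the shift is 0.0696·(0 − 0.04) = −0.3 points. With children at 20% and adults at 3%, it is 0.0696·(0.03 − 0.20) = −1.2 points, but a 20% null rate is far from the 4% that the SAP assumes.

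**The case against.** The strongest reply is that nothing rests on this analysis. It is labelled supportive, its p-values are unadjusted, adults are included for an initial exploration (SAP 3.2), and the pediatric and adult response rates are both reported separately, so no age difference is hidden. Randomization is central and stratified, about 4 adults per comparison group are planned, and Protocol 2.3.2 reports 12 adults randomized. The widening is conservative. All of this stands, and it is why the point is minor.

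It can also be said that if adults respond very differently there is no common risk difference to estimate. That is fair. But the Mantel-Haenszel figure is still a defined weighted average of the two age-specific differences, and at 4:4 the crude figure is the same average with a less efficient interval.

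Several stronger readings are tempting, and the documents do not support them:
- **That any adult imbalance biases the result.** Stratified randomization leaves no systematic bias. A chance imbalance matters only if age is prognostic or modifies the effect. Block size and the adult counts by arm are not stated.
- **That the trial expects adults to respond less.** Protocol 4.2.1 reports an earlier trial's result; it sets no adult rate for this one.
- **That all four endpoints have a faulty interval.** For the secondary endpoints 7.8.2 displays p-values only. Adult balance is not protected in the multi-allergic subset used for two of them, but there is no displayed interval to correct.
- **That a stratified exact test would gain power.** With children at 46.4% or 32% against 3.2% (the SAP rates times 0.8 for dropout), and adults at 10% against 3%, a plain stratified exact test has power 0.899 (high) and 0.605 (low). Fisher has 0.903 and 0.625. A gain appears only with a mid-P version, which gives up Fisher's guaranteed size.

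**Conclusion.** The point holds as a minor one. The all-subjects analysis of the primary endpoint omits the randomization stratum, and no other planned all-subjects analysis adjusts for age. At the planned 20 + 4 per group the cost is an interval about 0 to 8% wider by the Wald calculation (1 to 4% for Newcombe), at most about 1.6 points on a half-width of about 21. The cost vanishes on the Wald scale if adults respond like children. There is no shift at 4:4:4, and roughly 0 to 2 points (2.3 at the extreme examined) at 5:3.

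These sizes rest on assumed adult response rates, on the SAP's child rates, and on a 5:3 split that is hypothetical. A reader might infer that the primary conclusion or its power is weakened. Neither is, because both are confined to the pediatric stratum.

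**What to change.** In the Supportive Analyses paragraph of SAP 7.8.1, specify that the all-subjects comparison of each dose with pooled placebo on the primary endpoint reports the Mantel-Haenszel risk difference stratified by randomized age group, with stratified Newcombe limits. Place it beside the pediatric and adult results already planned. Keep Fisher's exact test for the p-values, here and for the secondary endpoints, and leave the pediatric primary analysis unchanged.

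The cost is a sentence in the SAP and a few lines of code. It needs no new data and has no effect on the primary test or sample size.

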6.7. Subgroups

Although the general analysis will be presented by treatment group, subgroup analysis of the primary and secondary endpoints may be provided for the following:

- Age Group (pediatric subjects \geq 4 to $<$ 18 years of age, and adult subjects \geq 18 to \leq 55 years of age) according to the randomization stratification. No hypotheses testing will be performed in adult group; only descriptive statistics will be provided for this group.
- Target Maintenance Dose Group includes subjects who achieved their assigned target dose during the treatment stage and maintained this dose through the Exit Food Challenge/Week 40 Visit. These subjects will be analyzed according to their randomized treatment dose as the following:
 - Subjects who reached 1500 mg of study drug (low-dose group) – Yes or No
 - Subjects who reached 4500 mg of study drug (high-dose group) – Yes or No

Achievement of the target maintenance dose will be captured by a flag (Y/N) in the database. The target dose level may be the same as the maintenance dose level for those subjects who reach their target dose and maintain it for at least two weeks prior to the Exit Food Challenge/Week 40 Visit.

7. Statistical Methods

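### The target-dose subgroup tests against placebo (explicit for the secondary endpoints, implied for the primary) condition on a post-randomization outcome and favour ADP101

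*SAP*

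**What the plan says.** SAP 6.7 defines a Target Maintenance Dose Group that "includes subjects who achieved their assigned target dose during the treatment stage" and held that dose to the Week 40 visit. Subjects are classed Yes or No within their randomized dose. The section says only that such subgroup analyses may be provided. It limits the adult subgroup to descriptive statistics and sets no such limit for the target-dose subgroup.

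The two efficacy sections go further:

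- **SAP 7.8.1** commits to analysing the primary endpoint in "Subgroups of ITT subjects who reached their target dose as their maintenance dose" and to plotting response by reached target dose. It names no test for this subgroup. SAP 6.6 makes pooled placebo the general comparator, so a comparison with placebo is implied.
- **SAP 7.8.2** repeats the secondary analyses in "subjects who reached 1500 mg of study drug for low-dose group, and subjects who reached 4500 mg of study drug for high-dose group". The method is that of the primary endpoint, which is Fisher's exact test against pooled placebo, and the Fisher p-values are displayed. SAP 6.1 adds: "All tests of treatment effect will be conducted at a 2-sided alpha level of 0.05".

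Neither document says that attainment depends on treatment, adjusts for it, or states whether pooled placebo is restricted to placebo subjects who reached target. The estimand section of SAP 7.8.1 treats study discontinuation as the only intercurrent event; failure to reach target is not one.

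**The concern.** Entry requires dose-limiting symptoms at 100 mg or less of at least one food (Protocol 5.1). An ADP101 subject at target takes 100 mg or 300 mg of each food every day, and allergic reactions lead to held, reduced or stopped dosing (Protocol 6.5.1 and 6.5.2). Reaching target on ADP101 is therefore itself a sign of allergen tolerance, which is close to what the exit challenge measures. Placebo contains 0 mg of protein (Protocol 6.1), so reaching target on placebo says almost nothing about the reaction threshold.

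Restricting the analysis to attainers keeps the more tolerant part of the ADP101 arm and nearly the whole placebo arm. Restricting both arms by the same rule does not restore the balance given by randomization. The subgroup also removes ADP101 dosing failures, whom the ITT analysis counts as non-responders if they have no exit challenge. What is at stake is an inflated subgroup difference, with a p-value beside it, that can be read as the benefit of reaching the full dose.

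**Working it through.** **1. The plan's own figure.** Inputs from SAP 3.2: "Assuming placebo response rates of 4% and active response rates of 40% and 58% in the low- and high-dose regimen treatment groups", 16 evaluable subjects per active arm, pooled placebo of 16 (8 + 8), alpha 0.05. Exact enumeration of two-sided Fisher tests gives 90.9% power for at least one dose under Simes (smaller p ≤ 0.025, or both ≤ 0.05) and 90.0% under Holm (smaller p ≤ 0.025). The stated 90% is reproduced. The 20% dropout allowance also reproduces: 48/0.8 = 60. Neither figure depends on the target-dose subgroup.

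**2. Upper-end illustration with no desensitising effect.** Let p be the proportion who would pass the exit challenge in either arm, and q the proportion of the remaining ADP101 subjects who still reach target. Assume that all would-be passers on ADP101 and all placebo subjects reach target. Then:

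- attainment on ADP101 = p + (1 − p)q
- response among ADP101 attainers = p / [p + (1 − p)q]
- response among placebo attainers = p

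The last column is the chance of a two-sided Fisher p ≤ 0.05 favouring ADP101, by exact enumeration, with 20 ADP101 pediatric subjects randomized (a random number of whom attain) and 20 on pooled placebo.

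| p | q | ADP101 attainers | Placebo | Chance of p ≤ 0.05 |
|---|---|---|---|---|
| 4% (SAP 3.2) | 40% | 0.04/(0.04 + 0.96×0.4) = 9.4% | 4% | 2.8% |
| 4% (SAP 3.2) | 30% | 0.04/(0.04 + 0.96×0.3) = 12.2% | 4% | 5.0% |
| 20% (assumed) | 40% | 0.20/(0.20 + 0.80×0.4) = 38% | 20% | 15% |
| 20% (assumed) | 30% | 0.20/(0.20 + 0.80×0.3) = 45% | 20% | 23% |

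An unselected comparison would give a difference of 0 in every row. The values of q and the 20% rate are assumptions, and 20% is five times the SAP's figure.

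**3. Imperfect correlation.** Let dosing tolerance and exit threshold be bivariate normal with correlation rho. On ADP101 the top fraction r in dosing tolerance reaches target. On placebo 90% do, independently of threshold. With p = 4% and rho = 0.6:

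| ADP101 attainment r | ADP101 attainers | Excess over 4% | Ceiling 4%/r |
|---|---|---|---|
| 60% | 6.5% | +2.5 points | 6.7% |
| 40% | 9.0% | +5.0 points | 10% |
| 20% | 14.1% | +10.1 points | 20% |
| 10% | 20.1% | +16.1 points | 40% |

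With rho = 0 the excess is 0. Here r, rho and the 90% are assumptions; the documents give none of them.

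**4. If ADP101 works as assumed.** With a 58% response in the whole high-dose arm and 60% attainment, the rate among attainers can lie anywhere from (0.58 − 0.40)/0.60 = 30% to 0.58/0.60 = 96.7%. The upper value applies if every responder is an attainer.

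**The case against.** **The text for the primary endpoint is thin.** SAP 7.8.1 names no Fisher test, p-value or difference for this subgroup, and SAP 6.7 says only that subgroup analyses may be provided. This stands. A reader might infer a committed primary-endpoint test among attainers; the documents support that only by implication, through SAP 6.6. The comparison is explicit only for the secondary endpoints.

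**Non-attainers are classed too.** SAP 6.7 uses a Yes/No split and SAP 7.8.1 already plans plots by it. This also stands, and the fix builds on it. It does not rescue the Fisher tests in SAP 7.8.2.

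**The size may be small.** A reader might infer a gap of 18 to 25 points from the 20% rows. The SAP's planning rate does not support that: at 4% the gap is about 5 to 8 points, with at most about a 5% chance of a significant result in step 2. Attainment can also fail for reasons unrelated to tolerance, such as taste or volume of the product (SAP 7.8.1) or being unable to attend updosing visits (Protocol Appendix 6). Such reasons weaken the correlation and shrink the bias.

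**An inert product would show no bias.** Correct. A reader might take the point as holding with no drug effect of any kind. It requires that ADP101 provokes dosing reactions while failing to desensitise.

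**A caveat might be enough.** Only in part. The selection component depends on a correlation that the data cannot identify, so a caveat would not tell a reader how much of the difference to discount.

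**Conclusion.** The repeated Fisher tests in SAP 7.8.2, and any matching comparison implied for the primary endpoint, are biased toward ADP101. This rests on two conditions: dosing reactions limit attainment on ADP101, and dosing tolerance is correlated with the exit threshold. Both are plausible from the protocol's entry and dose-modification rules, but neither is quantified in the documents.

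At the SAP's 4% rate the upper-end illustration gives 9.4% or 12.2% against 4%. The bias is smaller with imperfect correlation, and larger with a higher background rate or much lower attainment. That 4% was set for the 600-mg primary endpoint; no placebo rate is given for the secondary endpoints, where the test is explicit. The harm is mainly a biased estimate and an uninterpretable p-value, rather than a large false-positive rate.

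A reader might infer that the trial's main conclusion is compromised. It is not. The primary analysis uses all pediatric ITT subjects with Holm adjustment, the rule for claiming significance in SAP 3.2 concerns only the primary endpoint, and the 90% power figure is unaffected.

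**What to change.** - Remove the target-dose subgroup from the analyses repeated in SAP 7.8.2.
- For the primary and secondary endpoints, report response by attained target dose (Yes/No) descriptively within each arm, without p-values or differences from placebo. Say so in SAP 6.7 and 7.8.1, as is already done for adults. Keep the planned plots.
- State that attainment is a post-randomization outcome affected by treatment, so differences between attainers on ADP101 and on placebo are not treatment effects.

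If the effect among subjects able to reach target is itself of interest, define it as a principal-stratum estimand with its assumptions stated.

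The cost is a few sentences and fewer tests. The sponsor gives up a subgroup p-value that has no valid causal reading.
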